6.2. Endpoints

6.2.1. Primary Efficacy Endpoint

- Annualized rate of VOCs

VOC is defined as a documented episode of an acute painful crisis (for which there was not an explanation other than VOC) that involves moderate to severe pain lasting for at least 2 hours and at least one of the following:

- Use of escalated analgesia (including healthcare professional-instructed use of an analgesic prescription)

- A hospital, emergency department, or clinic visit and/or healthcare telephone consultation at the time of occurrence
- Diagnosis of ACS (defined as an acute illness characterized by fever and/or respiratory symptoms, accompanied by a new pulmonary infiltrate on a chest X-ray), hepatic sequestration, splenic sequestration, or priapism (in males)

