12.1.2.1.2. Definition of a Serious Adverse Event

An SAE is any AE that results in one or more of the following outcomes:

- **Death**
- **Requires or prolongs hospitalization** (In general, hospitalization signifies that the subject has been detained, usually involving at least an overnight stay, at the hospital or emergency ward for observation and/or treatment that would not have been appropriate in the physician's office or outpatient setting. Complications that occur during hospitalization are AEs. If a complication prolongs hospitalization or fulfills any other serious criteria, the event is serious. When in doubt as to whether "hospitalization" occurred or was necessary, the AE should be considered serious.)
- **Is life-threatening** (In general, an AE is considered to be life-threatening if the subject is at immediate risk of death. It does not include an AE that, had it occurred in a more severe form, might have caused death.)
- **Persistent or significant disability/incapacity** (In general, this means a substantial disruption of a person's ability to conduct normal life functions. This definition is not intended to include experiences of relatively minor medical significance such as uncomplicated headache, nausea, vomiting, diarrhea, influenza, or accidental trauma [e.g., sprained ankle] that may interfere with or prevent everyday life functions, but do not constitute a substantial disruption.)
- **Congenital anomaly or birth defect** (that occurs in the offspring of a subject exposed to the investigational product)
- **Other medically important event** (In general, this means an AE that, based upon appropriate medical judgment, is considered to jeopardize the subject's safety and may require medical or surgical intervention to prevent one of the outcomes listed above.)

Reporting requirements for SAEs are described in Section [12.1.2.3](#).

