12.1.2.2. Evaluation of Adverse Events/Serious Adverse Events

12.1.2.2.1. Assessment of Severity

AE severity (intensity) will be graded using National Cancer Institute Common Terminology for Adverse Events (NCI CTCAE), version 5.0 ([Appendix 2](#)). The CTCAE is a descriptive terminology utilized for AE reporting. A grading scale is provided for each AE term.

Grade refers to the severity (intensity) of the AE. The CTCAE provides unique clinical descriptions of severity for each AE based on the following general guideline:

- Grade 1** Mild; asymptomatic or mild symptoms; clinical or diagnostic observations only; intervention not indicated
- Grade 2** Moderate; minimal, local or noninvasive intervention indicated; limiting age-appropriate instrumental ADL*
- Grade 3** Severe or medically significant, but not immediately life-threatening; hospitalization or prolongation of hospitalization indicated; disabling; limiting self-care ADL**
- Grade 4** Life-threatening consequences: urgent intervention indicated
- Grade 5** Death related to AE

ADL = activities of daily living; AE = adverse event; CTCAE = Common Terminology Criteria for Adverse Events

*Instrumental ADL refer to preparing meals, shopping for groceries or clothes, using the telephone, managing money, etc.

**Self-care ADL refer to bathing, dressing and undressing, feeding self, using the toilet, taking medications, and not bedridden.

Note: The CTCAE terminology provides grading for specific laboratory test abnormalities ([Appendix 2](#)). Grade 4 laboratory abnormalities do not automatically signify life-threatening AEs. Abnormal laboratory test results will be considered AEs only if the investigator, based on his or her medical judgement, deems the abnormality to be clinically significant.

Change in severity of an AE should be documented based on specific guidelines in the eCRF Completion Guidelines.

Severity and seriousness must be differentiated: Severity describes the intensity of an AE, while the term seriousness refers to an AE that has met the criteria for an SAE (defined in Section [12.1.2.1.2](#)).

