9.2 Safety Endpoints

Safety endpoints include the number and percentage of subjects with the following:

- At least one treatment-emergent adverse events (AEs)
- At least one treatment-emergent serious adverse events (SAEs)
- At least one clinically significant change in a laboratory test parameter
- At least one clinically significant change in a vital signs parameter
- At least one clinically significant change in an electrocardiogram (ECG) parameter

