13.5.4 Other Secondary Endpoints

Proportion of VOC-free subjects

VOC-free subjects are defined as these who did not experience a VOC after the first dose of study drug through the end of treatment. Proportion of VOC-free subjects will be analyzed using a stratified Cochran-Mantel-Haenszel (CMH) test adjusted for stratification factors of region (North America/Europe vs. Africa/Middle East) and HU use (Yes vs. No) using the ITT analysis set. Sensitivity analysis will be performed for proportion of VOC-free subjects using the PP analysis set.

Annualized rate of VOC-related hospitalizations

Annualized rate of VOC-related hospitalization is calculated as total number of VOC-related hospitalizations / ([Date of last dose of study drug – date of first dose of study drug + 1] / 365.25).

VOC-related hospitalization will be determined from the “Adverse Event” CRF when the AE’s preferred term = “sickle cell anaemia with crisis” and “Did the adverse event result in initial or prolonged hospitalization for the subject?” = “Yes”. Date of last dose of study drug are collected from “End of Treatment” CRF page. If that date is not available (which is expected for some of the subjects in IA), the data cut-off date will be used.

VOC-related hospitalization-free subjects are defined as these who did not experience a VOC-related hospitalization after the first dose of study drug through the end of treatment.

Analyses of annualized rate of VOC-related hospitalizations will be done in the same way as in [Section 13.5.2](#) as for the primary endpoint (annualized rate of VOCs).

Annualized rate of days hospitalized for VOC-related hospitalizations

Annualized rate of days hospitalized for VOC-related hospitalizations is calculated as (sum of total number of days hospitalized for VOC-related hospitalization / ([Date of last dose of study drug – date of first dose of study drug + 1] / 365.25)).

Number of days hospitalized for VOC-related hospitalization is calculated as the sum of (Date of Discharge – Date of Admission + 1) for all AEs with preferred term = “sickle cell anaemia with crisis” and “Did the adverse event result in initial or prolonged hospitalization for the subject?” = “Yes”.

Date of last dose of study drug are collected from “End of Treatment” CRF page. If that date is not available (which is expected for some of the subjects in IA), the data cut-off date will be used.

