13.5.5 Exploratory Efficacy Endpoints

The analysis of change (and percentage change) from baseline in renal function at Week 24 and Week 52 will be similar to the analysis of other change from baseline efficacy variables. Change from baseline will be calculated for each of the following renal function parameters at Week 24 and Week 52 separately:

- Urine protein-to-creatinine (Pr:Cr) ratio
 - Urine Microalbumin
 - Urine ACR (albumin to creatinine ratio)
- Urine Cystatin C

Line plots will be provided for LS mean change +/- SE.

Additional exploratory analysis (which are not specified in protocol) will be performed if the data allow, as shown in, but not limited to, the list below. In general, the exploratory endpoints will be analyzed following the same analysis approach specified for similar endpoints specified in primary and secondary analysis sections at FA, unless otherwise specified.

VOC Analyses:

- Number and percentage of subjects with at least 1 VOC event

- Number and percentage of subjects by category of number of VOC events: 0, 1, 2-4, 5-7, 8-12, 13+
- Number of and percentage of subjects with at least one VOC event lasting for \geq 48 hours
- Number and percentage of subjects with complicated VOCs (ACS, priapism, hepatic or splenic sequestration)
 - Number and percentage of subjects with at least 1 ACS
 - Number and percentage of males with priapism
 - Number and percentage of subjects with hepatic or splenic sequestration
- Number of and percentage of subjects with uncomplicated VOCs
- Time to first event of complicated VOCs
- Annualized rate of days of VOCs (days)
- Annualized VOC rate, excluding subjects with a short period of exposure (< 4 weeks)
- Annualized rate of uncomplicated VOCs

VOC-Related Hospitalizations:

- Number and percentage of subjects with at least 1 VOC-related hospitalization
- Number and percentage of subjects by category of number of VOC-related hospitalizations: 0, 1, 2-4, 5-7, >7.

RBC Transfusions:

- Time to first RBC transfusion
- Number and percentage of subjects with at least 1 RBC Transfusion

Relationships between biomarkers

- Pairwise correlation (Pearson correlation coefficients and p-values) of annualized rate of VOCs and PD parameters (e.g., HbF, Total Hb, F-cells) will be tabulated for Week 24 and Week 52, and for HU and non-HU use separately and together. Corresponding scatter plots will also be provided.

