TEAEs leading to dose reduction will be identified by action taken with study treatment being recorded as “Dose Reduced” on the Adverse events CRF.

Overall Summary

An overall summary of TEAEs will be presented by treatment group for the safety analysis set. The number and percentage of subjects reporting any of the following categories will be provided:

- Any pre-treatment adverse event
- Any TEAE
- Grade 3 or higher TEAEs
- Treatment-related TEAEs
- Treatment-related grade 3 or higher TEAEs
- Treatment-related grade 2 or higher TEAEs
- SAEs
- Treatment-related SAEs
- Treatment-related grade 3 or higher SAEs
- TEAEs leading to death

- TEAEs leading to discontinuation of study drug
- Treatment-related TEAEs leading to discontinuation of study drug
- TEAEs leading to study discontinuation
- Treatment-related TEAEs leading to study discontinuation
- TEAEs leading to dose reduction
- Treatment-related TEAEs leading to dose reduction

The following AE summaries will be by treatment group, SOC and PT for the safety analysis set. SOCs will be sorted alphabetically and PTs will be sorted by descending frequency in the pooled IMR-687 treatment group column, and then alphabetically for ties.

- The number and percentage of subjects with any TEAE. The AE count will be for subjects not events, and subjects are only counted once within each SOC or PT
- The number and percentage of subjects with Grade 3 or higher TEAEs
- The number and percentage of subjects with Treatment-related TEAEs. Subjects with multiple events within a particular SOC or PT will be counted under the category of their most drug-related event within that SOC or PT (related or not related). AEs will be considered related to study drug if they are reported as certain/related, probably/likely related, or possibly related.
- The number and percentage of subjects with Treatment-related TEAEs
- The number and percentage of subjects with Treatment-related Grade 3 or higher TEAEs
- The number and percentage of subjects with Treatment-related Grade 2 or higher TEAEs
- The number and percentage of subjects with SAEs
- The number and percentage of subjects with Treatment-related SAEs
- The number and percentage of subjects with Treatment-related Grade 3 or higher SAEs
- The number and percentage of subjects with TEAEs leading to death
- The number and percentage of subjects with TEAEs leading to discontinuation of study drug

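### Hospitalized VOCs are SAEs, so the any-SAE row mixes efficacy with toxicity, and the SAP text lists no count of subjects with an SAE other than a crisis

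*SAP*

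**What the plan says.** **Where hospitalized VOCs are recorded.** In SAP 13.5.4, "VOC-related hospitalization will be determined from the" Adverse Event CRF: the preferred term is sickle cell anaemia with crisis, and the hospitalization question is answered Yes. So a hospitalized VOC is an AE record.

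**Whether they are serious.** One SAE criterion in Protocol 12.1.2.1.2 is that the event "Requires or prolongs hospitalization". Protocol 12.1.2.3 collects SAEs whatever the investigator thinks of causation. Neither section exempts VOCs or other disease-related events. Protocol 8.7 expects that AEs of the underlying disease can be SAEs.

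**Severity.** The general guideline for Grade 3 in Protocol 12.1.2.2.1 includes "hospitalization or prolongation of hospitalization indicated".

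**What is tabulated.** SAP 9.2 makes the number and percentage of subjects with at least one treatment-emergent SAE a safety endpoint. SAP 13.5.8.1 identifies SAEs by the CRF seriousness question alone. For the overall summary it states: "An overall summary of TEAEs will be presented by treatment group for the safety analysis set". The rows include any TEAE, Grade 3 or higher TEAEs and SAEs, and none of them excludes crises. The same section also plans:
- SAE and Grade 3 or higher tables by SOC and preferred term, under the convention that "subjects are only counted once within each SOC or PT";
- treatment-related versions of these rows and tables;
- listings of all AEs and SAEs.

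SAP 13.5.5 adds, on the efficacy side, "Number and percentage of subjects with at least 1 VOC-related hospitalization".

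**The concern.** One event type feeds both sides of the benefit-risk comparison. Hospitalized crises count towards the VOC efficacy endpoints and also towards the SAE endpoint that serves the primary safety objective. If the drug lowers VOCs as planned, the any-SAE row improves on drug for efficacy reasons. A reader of that row alone could see parity, or an advantage for drug, while other SAEs are more frequent on drug. The Grade 3 or higher row probably behaves the same way, but that is an inference from the general grading guideline. At stake is how one headline safety row is read in the clinical study report and by the DMC.

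**Working it through.** The plan states no figure on this point, so there is none to reproduce. The SAE status follows from the definitions above. The arithmetic only illustrates how far the aggregate row could move.

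**Inputs from the documents (SAP 8.1.2).** VOC rates m of 5.0 (placebo) and 3.0 (highest tolerated dose) a year; SD 2.7.

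**Assumed, not in the documents.** Share s of VOCs hospitalized, 10% to 50%; non-crisis SAE risk q in each arm; independence of the two kinds of SAE.

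**Step 1. Probability v of at least one hospitalized VOC in a year.**
- Poisson: v = 1 − exp(−m·s). At s = 10%: 1 − e^(−0.5) = 39.3% v 1 − e^(−0.3) = 25.9%.
- Negative binomial: v = 1 − (k/(k + m·s))^k. From the placebo rate and SD, k = 25/(2.7² − 5) = 10.9, used in both arms. At s = 10%: 38.7% v 25.6%.

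For s from 10% to 50%, the gap in favour of drug is 13.4 to 18.3 points (Poisson) or 13.1 to 17.6 (negative binomial, common k). It is 14.2 to 22.8 if the SD is 2.7 in each arm, which makes k = 9/(2.7² − 3) = 2.1 on drug. With 25% dropout spread evenly over the year, the overall range is about 12 to 21.5 points.

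**Step 2. Any-SAE row = 1 − (1 − v)(1 − q).** Negative binomial with common k, rounded at the end, placebo v drug:

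| s | ≥1 hospitalized VOC, % | any-SAE row, %, if q = 10% v 10% | any-SAE row, %, if q = 10% v 25% |
|---|---|---|---|
| 10% | 38.7 v 25.6 | 44.8 v 33.1 | 44.8 v 44.2 |
| 20% | 61.6 v 44.2 | 65.4 v 49.8 | 65.4 v 58.2 |
| 30% | 75.5 v 57.9 | 77.9 v 62.1 | 77.9 v 68.4 |
| 50% | 89.5 v 75.5 | 90.5 v 77.9 | 90.5 v 81.6 |

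In the last column, a true 15-point excess of non-crisis SAEs reads as level at s = 10% and as a benefit of 7 to 10 points at the higher shares.

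**Step 3. Break-even.** The two arms read the same when 1 − q(drug) = (1 − q(placebo)) × (1 − v(placebo))/(1 − v(drug)). Under Poisson, the last ratio is e^(−2s). With q = 10% on placebo and s = 10%, q on drug is 1 − 0.9 × 0.819 = 26.3%. So an excess of up to about 16 points would leave the row at parity or in favour of drug.

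**Step 4. No VOC effect.** With 5.0 VOCs a year in both arms and s = 20%, the row difference is e^(−1) × 15 = 0.368 × 15 = 5.5 points. The excess is then diluted but not reversed.

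**Step 5. What the planned tables still show.** A subject is counted once within each preferred term, so every non-crisis term counts all subjects who had that SAE, whether or not they also had a crisis. The same holds for every SOC row except the one that contains the crisis term. These rows do not carry the crisis effect. They cannot be added to give subjects with at least one non-crisis SAE, because one subject can appear in several rows.

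**The case against.** The strongest reply is that the separation is largely there already. The SAE and Grade 3 or higher tables by SOC and preferred term show each non-crisis event by arm. The treatment-related rows remove crises that the investigator judged unrelated. The listings hold every SAE. Under Protocol 7.2 the DMC may see unblinded SAE data, and its chair receives every SAE report. Safety is descriptive and Protocol 8.7 sets no SAE-frequency stopping rule, so deriving the count later costs no type I error.

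Most of this stands, and it limits the point to one aggregate. A reader might infer that the plan cannot tell toxicity from efficacy, or that an excess of other SAEs would go unseen. The documents do not support that, because the effect is confined to the aggregate rows and the SOC row holding crises. Nor do they show that no such display exists anywhere. The table shells (SAP Appendix 8) and the DMC charter are separate documents that were not available, so the statement covers only the SAP text.

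Two further objections also stand. First, independence is doubtful. Protocol 12.1.2.1.2 treats complications during a hospital stay as AEs, serious if they prolong it, so fewer VOC admissions on drug may also lower SAEs under other terms. Second, excluding one preferred term does not remove the efficacy effect, because the VOC definition in Protocol 6.2.1 includes "Diagnosis of ACS (defined as an acute illness characterized by fever and/or respiratory symptoms", together with sequestration and priapism, and these may be coded elsewhere.

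What remains is that treatment-related rows rest on causality judgement and give no all-cause comparison. Subtracting the crisis row from the any-SAE row, which the SAP does not plan, would give only subjects whose SAEs were all non-crisis.

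**Conclusion.** The point holds as a small reporting improvement. Hospitalized VOCs are SAEs under the protocol's definition, at least one SAE is a named safety endpoint, and SAP 13.5.8.1 lists no aggregate count of subjects with an SAE other than a crisis. At the planned VOC effect, the any-SAE row would favour drug by about 12 to 20 points with equal non-crisis risks of 10% (step 2 formula, across the three count models). It could hide a rise from 10% to 25%.

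These sizes depend on the assumed hospitalized share, the assumed non-crisis risks, independence, and a VOC effect as large as planned. The SAE part follows from the text, and the Grade 3 or higher part is probable. The any-TEAE row is a weaker case, because the documents do not say whether non-hospitalized VOCs are AE records. No hypothesis test, stopping rule or data collection is affected.

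**What to change.** Keep every planned table. In SAP 13.5.8.1, beside the existing SAE and Grade 3 or higher rows, pre-specify a second row for each, labelled as excluding the preferred term sickle cell anaemia with crisis. Provide both for the clinical study report and the DMC. The rule uses the preferred term alone, so no matching to the VOC CRF page is needed.

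Footnote that acute chest syndrome, hepatic or splenic sequestration, priapism and complications of VOC admissions coded to other terms remain in these rows, so they are not free of the efficacy effect. A matching any-TEAE row is optional.

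The cost is two extra rows from AE data already collected and coded, and a second set of totals to explain. If the table shells already contain such rows, only the SAP text needs to say so.

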13.5.8.2 Laboratory Data

Clinical laboratory tests (serum chemistry, hematology, urinalysis, and specialty hematology) will be summarized using the safety analysis set. Results will be evaluated and presented using the International System of Units (SI units) unless otherwise stated. Clinical laboratory values will be graded from Grade 1 to Grade 4 using NCI CTCAE, version 5.0. Post-baseline laboratory values will only be compared to baseline values from the same source. For example, if the baseline value for a parameter came from a local laboratory, post-baseline results from the same local laboratory should be used for the analysis.

Hematology assessments include: RBC count (mean corpuscular volume [MCV], mean corpuscular Hb, and mean corpuscular Hb concentration), hematocrit, Hb, platelets, WBC count (with differential: basophils, eosinophils, neutrophils, monocytes, and lymphocytes), erythrocyte count, and reticulocyte count and reticulocyte percentage. Some of these assessments are also considered PD endpoints, and further detailed in the secondary and exploratory endpoint sections above.

Specialty hematology assessments include: HbF and percent F-cells.

Coagulation assessments include: PT, aPTT, and international normalized ratio (INR).

Serum chemistry assessments include: alanine aminotransferase (ALT), albumin, alkaline phosphatase (ALP), aspartate aminotransferase (AST), bicarbonate, blood urea nitrogen (BUN), chloride, calcium, creatinine, glucose, lactate dehydrogenase (LDH), sodium, potassium, magnesium, phosphate, bilirubin (total, direct, and indirect), creatine kinase, total protein, glomerular filtration rate (GFR), and gamma-glutamyl transferase (GGT). Follicle stimulating hormone (FSH) will be included as well, but this is only collected for post-menopausal women at screening. Some of these assessments are also considered PD endpoints, and further detailed in the secondary and exploratory endpoint sections above.

Urinalysis assessments include: appearance, color, pH, specific gravity, ketones, protein, glucose, bilirubin, and urobilinogen, including occult blood and microscopic examination of sediment (only if occult blood is detected).

The laboratory results and change from baseline will be summarized by visit by treatment group for central laboratory continuous hematology, serum chemistry and urinalysis parameters separately. Note that character urinalysis tests will only be listed.

Shift tables representing the shift from the baseline grade to maximum NCI-CTCAE Grades (Grade I to IV and Missing) will be provided for selected hematology and chemistry parameters by visit by treatment group. See [Appendix 5](#) for details.

Potentially clinically significant (PCS) Criteria for hepatic function and renal function are shown in [Table 9](#) below. The number and percentage of subjects meeting these PCS criteria will be summarized for hepatic function parameters (ALT, AST, ALP, and total bilirubin) and the renal function parameter (serum creatinine) separately. Any subject with any post-baseline result (including “unscheduled” visits) meeting the criteria will be included in the tabulation.

Table 9 PCS Criteria for Hepatic Function and Renal Function

| Hepatic Function | Renal Function |
|--|---|
| 
 ○ Post-baseline Alanine Aminotransferase (ALT) $\geq 3 \times$ upper limit of normal (ULN) ○ Post-baseline Aspartate Aminotransferase (AST) $\geq 3 \times$ ULN ○ Post-baseline Direct Bilirubin (BILDIR) $\geq 2 \times$ ULN ○ Post-baseline ALT/AST and BILDIR (ALT $\geq 3 \times$ ULN or AST $\geq 3 \times$ ULN) and BILDIR $\geq 2 \times$ ULN (Hy's Law) | 
 ○ Post-baseline Creatinine Clearance (CREATCLR) $< 0.5 \times$ baseline ○ Post-baseline Serum Creatinine (CREAT) $> 2 \times$ baseline |

Creatinine clearance are not directly collected and will be calculated using the Crockroft Gault formula:

$$CrCl = \frac{(140 - \text{patient's age in years}) \times \text{Body weight in kg}}{72 \times \text{serum creatinine in mg/dl}}$$

All laboratory parameters (serum chemistry, central laboratory hematology, local laboratory hematology, specialty hematology, coagulation, and urinalysis) will be displayed in individual subject data listings.

